11.4.1. Analysis Populations

The Safety Analysis population includes all pregnant women who received the study vaccination, and all infants born during the study.

The maternal intent-to-treat (ITT) population for immunogenicity analyses includes all pregnant women who received the study vaccination.

The maternal per-protocol (PP) population for immunogenicity analyses includes all subjects in the ITT subset with the following exclusions:

- Data from all available visits for subjects:
 - Found to be ineligible at baseline.
 - Without results from the baseline visits.
 - Without results from at least one post-vaccination visit.
- Data from all visits subsequent to major protocol deviations, such as:
 - Receipt of non-study licensed vaccine within the pre-specified exclusion windows ([Section 5.2](#)).
 - Receipt of immunosuppressive therapy (e.g., corticosteroids) within 30 days prior to or after study vaccination.
- Data from any visit that occurs substantially out of window.

The infant ITT population for immunogenicity analyses includes all infants born to women who received the study vaccination.

The infant PP population for *primary and secondary* immunogenicity analyses includes all infants in the ITT subset who have a blood sample from the perinatal period (cord blood or drawn blood within the 72 hours after birth).

The infant PP population for *exploratory* immunogenicity analyses includes all infants in the ITT subset with the following exclusions:

- Infants who did not receive DTwP within appropriate window.
- Infants who received any product that would impact immune response.
- Infants with blood samples captured substantially out of window.

In the case of mis-randomization, subjects will be analyzed according to the study product actually received for all analysis populations.

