#### 3.2.2. Secondary

##### Immunogenicity:

- Maternal humoral immunity: GMC of serum IgG antibodies to Tdap vaccine antigens (PT, FHA (Filamentous Hemagglutinin), PRN (Pertactin), tetanus, diphtheria) as measured by ELISA in pregnant women one month after receipt of BOOSTRIX or Td, at the time of delivery, and 6 months after delivery.
- Infant humoral immunity: GMC of serum IgG antibodies to Tdap vaccine antigens (PT, FHA, PRN, tetanus, diphtheria) as measured by ELISA at birth and prior to receipt of first DTwP (approximately 6 weeks of age) among infants born to women vaccinated with BOOSTRIX compared to Td.

- Placental antibody transfer: The geometric mean ratio (GMR) of maternal and infant-specific Tdap-specific antibodies (PT, FHA, PRN, tetanus, diphtheria) as measured by ELISA at delivery after intrapartum receipt of BOOSTRIX versus Td.
- Interference with infant responses among infants whose mothers received intrapartum BOOSTRIX compared to Td: GMC of antibodies to DTwP vaccine antigens (PT, FHA, PRN, Fimbriae 2 (FIM2), Fimbriae 3 (FIM3), tetanus, diphtheria) as measured by ELISA one month after the first dose of DTwP (~10 weeks of age, ½ of infants), one month after the third dose of DTwP vaccine (~18 weeks of age, ½ of infants), and at 6 months of age.

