#### 6.3.2. Per Protocol (PP) Population

The maternal per-protocol (PP) population for immunogenicity analyses includes all subjects in the ITT subset with the following exclusions:

- Data from all available visits for subjects:
  - Found to be ineligible at baseline.
  - Without results from the baseline visits.
  - Without results from at least one post-vaccination visit.
- Data from all visits subsequent to major protocol deviations, such as:
  - Receipt of non-study licensed vaccine within the pre-specified exclusion windows ([Section 4.3.2](#)).

- Receipt of immunosuppressive therapy (e.g., corticosteroids) within 30 days prior to or after study vaccination.
- Data from any visit that occurs substantially out of window.

The infant PP population for *primary and secondary* immunogenicity analyses includes all infants in the ITT subset who have a blood sample from the perinatal period (cord blood or drawn blood within the 72 hours after birth).

The infant PP population for *exploratory* immunogenicity analyses includes all infants in the ITT subset with the following exclusions:

- Infants who did not receive DTwP within appropriate window.
- Infants who received any product that would impact immune response.
- Infants with blood samples captured substantially out of window.

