### 7.2. Protocol Deviations

A summary of subject-specific protocol deviations will be presented by the reason for the deviation, the deviation category, and treatment group for all enrolled mothers and infants ([Table 6](#) and [Table 7](#), respectively). Deviations that are considered major deviations that will be reviewed for possible subject exclusion from the per protocol population include: mother receipt of non-study licensed vaccine, mother receipt of immunosuppressive therapy, infant did not receive DTwP within window, infant received product that would impact immune response and infant blood samples captured substantially out of window. All subject-specific protocol deviations and non-subject specific protocol deviations will be included in [Appendix 3](#) as data listings ([Listing 2](#) and [Listing 3](#), respectively).

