### 8.2.4. Inference with infant responses among infants whose mothers received intrapartum BOOSTRIX compared to Td

Summaries and analysis of immunogenicity data will be presented by treatment group at one month after receipt of first DTwP, one month after receipt of third DTwP, and at 6 months of age. DTwP antibody concentrations to PT, FHA, PRN, FIM2, FIM3, tetanus and diphtheria, will be summarized. Analysis will include GMCs along with corresponding 95% confidence intervals. The GMC between treatment groups will be compared using a t-test on log-transformed ELISA titers (Table 23 and Table 24).

RCD curves for infants will be presented for DTwP antibody concentrations to PT, FHA, PRN, FIM2, FIM3, tetanus and diphtheria. Plots will be generated with three panels (One Month After Receipt of First Dose of DTwP, One Month After Receipt of Last Dose of DTwP, and 6 Months of Age), and separate curves within each panel for each treatment group, as shown in Figure 13, Figure 14, Figure 15, Figure 16, Figure 17, Figure 18, Figure 19, Figure 20, Figure 21, Figure 22, Figure 23, Figure 24, Figure 25, and Figure 26.

Log-transformed DTwP antibody concentrations for infants to PT, FHA, PRN, FIM2, FIM3, tetanus and diphtheria will be plotted over time by treatment group along with the geometric mean at each time point (Figure 67, Figure 68, Figure 69, Figure 70, Figure 71, Figure 72, Figure 73, Figure 74, Figure 75, Figure 76, Figure 77, Figure 78, Figure 79, and Figure 80). The GMCs and 95% confidence intervals of log-transformed serum IgG antibodies to each antigen will be plotted over time by treatment group in Figure 121, Figure 122, Figure 123, Figure 124, Figure 125, Figure 126, Figure 127, Figure 128, Figure 129, Figure 130, Figure 131, Figure 132, Figure 133, and Figure 134.

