## 8.3. Exploratory Immunogenicity Analyses

### 8.3.1. Maternal immunogenicity cofactors for maternal and neonatal anti-PT antibody responses following intrapartum BOOSTRIX

Summaries and analysis of immunogenicity data will be presented for maternal and infant subjects in the BOOSTRIX group for anti-PT antibody responses at time of delivery or birth, as applicable. Serum IgG antibody concentrations to PT will be summarized by maternal age (18-29, 30-39 years old), parity (primiparous vs multiparous), GA at time of vaccination (14-17, 18-21, 22-26 weeks), GA at time of delivery (28-32, 33-36, 37+ weeks), and infant birthweight. Analysis will include GMCs along with corresponding 95% confidence intervals ([Table 37](#), [Table 38](#), [Table 39](#), and [Table 40](#)).

Additionally, regression modelling will be employed to evaluate the association of log-transformed anti-PT antibody response with each of the stratified maternal cofactors defined previously, as well as with infant birthweight as a continuous variable. Separate models will be used for each analysis population and each cofactor. The analysis of variance model for a stratified cofactors is as follows,

$$\ln(titer) = \beta_0 + \beta_{1i}x_i + \varepsilon;$$

where  $\beta_0$  is the intercept,  $x_i$  is a categorical variable with  $i$  levels for a cofactor with  $i + 1$  levels,  $\beta_{1i}$  is the regression coefficient for each level of the covariate  $x_i$ , and  $\varepsilon$  is random error assumed to be normally distributed. The model will be constructed using reference cell coding; a single level of each cofactor will be used as the reference level and the parameter  $\beta_{1i}$  will be estimated for the remaining levels.

The model for the continuous cofactor of infant birthweight is as follows,

$$\ln(titer) = \alpha_0 + \alpha_1z + \varepsilon;$$

where  $\alpha_0$  is the intercept,  $\alpha_1$  is the regression coefficient,  $z$  is the continuous covariate, and  $\varepsilon$  is random error assumed to be normally distributed.

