**Table 12: Analysis Populations by Treatment Group – Infant Subjects**

Analysis Populations	Reason Subjects Excluded	BOOSTRIX (N=X)		Td (N=X)		All Subjects (N=X)	
		n	%	n	%	%	n
Infant Safety	Not born during the study period	x	xx	x	xx	x	xx
Infant Intent-to-Treat	Not born to a woman who received the study vaccination						
Infant Per Protocol	Any Reason						
	Did not contribute a valid perinatal blood sample*						
	Did not receive DTwP within appropriate window #						
	Received any product that would impact immune response #						
	Blood samples were captured substantially out of window #						

Note: N= Number of infant subjects enrolled; n=number of infant subjects meeting the criterion  
 \*Exclusion only from the primary and secondary immunogenicity analysis Infant Per Protocol population  
 #Exclusion only from the exploratory immunogenicity analysis Infant Per Protocol population

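### Infant per-protocol exclusions follow endpoint tier, not sampling time: the DTwP-interference PP table ignores the DTwP schedule, while the birth cofactor PP tables depend on it

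*SAP*

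**What the plan says.** Protocol 11.4.1 and SAP 6.3.2 give two infant PP definitions in the same words. The one for primary and secondary "immunogenicity analyses includes all infants in the ITT subset who have a blood sample from the perinatal period", meaning cord blood or a draw within 72 hours. The one for exploratory analyses starts from the ITT infants and removes three groups: "Infants who did not receive DTwP within appropriate window", those given a product that would affect the immune response, and those bled substantially out of window.

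The footnotes to SAP Table 12 make the split exclusive. The missing perinatal sample is marked "Exclusion only from the primary and secondary immunogenicity analysis Infant Per Protocol population". The DTwP, product and sampling-window reasons are marked "Exclusion only from the exploratory immunogenicity analysis Infant Per Protocol population".

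Two analyses matter here:

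- SAP 3.2.2 lists as a secondary endpoint "Interference with infant responses among infants whose mothers received intrapartum BOOSTRIX compared to Td: GMC of antibodies to DTwP vaccine antigens". SAP 8.2.4 analyses it "at one month after receipt of first DTwP, one month after receipt of third DTwP, and at 6 months of age", with Table 23 for ITT and Table 24 for PP.
- SAP 8.3.1, an exploratory analysis, covers subjects "in the BOOSTRIX group for anti-PT antibody responses at time of delivery or birth, as applicable". The infant PP results are Tables 40 and 44.

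SAP 7.2 lists the same three infant deviations as ones to be "reviewed for possible subject exclusion from the per protocol population", and names no tier.

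**The concern.** Whether a deviation disqualifies a measurement depends on when the sample was taken and what happened before it, not on whether the endpoint is called secondary or exploratory. Here the tiers and the time points do not line up. The post-DTwP analysis falls under the rule written for birth samples, and one birth analysis falls under the rule written for post-DTwP samples.

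The effect on infant immune responses is in the trial's title. A reader will take agreement between Tables 23 and 24 as evidence that the interference result is robust to infants vaccinated late or bled at the wrong time. As written, Table 24 removes none of those infants, so agreement would say nothing on that point. Anti-PT at birth in the BOOSTRIX arm would also be reported on one PP set in Table 22 and a different one in Tables 40 and 44.

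**Working it through.** **1. The rule applied to each analysis**

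| Analysis | Tier | Sample time | Exclusions the rule applies | Exclusions relevant to the sample |
|---|---|---|---|---|
| Anti-PT at birth, Table 22 | Primary | Birth | No perinatal sample | Same |
| DTwP interference, Table 24 | Secondary | 10 or 18 weeks; 6 months | No perinatal sample | DTwP timing, product, sampling window |
| Anti-PT cofactors, Tables 40 and 44 | Exploratory | Birth | DTwP timing, product, sampling window | No valid perinatal sample |
| Infant cytokines, Table 36 | Exploratory | Mainly post-DTwP | DTwP timing, product, sampling window | Broadly the same |

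The second and third rows are mismatched. In the third, DTwP starts at about 6 weeks and cannot affect a birth sample.

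**2. Can the situations arise?** Protocol 2.3.1 puts DTwP at 6, 10 and 14 weeks. An infant on the 18-week schedule has no study visit between 6 and 18 weeks (Protocol 4), so doses 2 and 3 fall outside study visits. Visit windows (Protocol 7.4.2.2) give Visit 06 on days 37–47 and Visit 07 on days 65–75 or 125–135.

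- 10-week sample after a dose 1 given at Visit 06: 65 − 47 = 18 to 75 − 37 = 38 days.
- 18-week sample after dose 3 on day 98: 125 − 98 = 27 to 135 − 98 = 37 days.
- Dose 3 given 28 days late (day 126): 125 − 126 = −1 to 135 − 126 = 9 days, so the sample could precede the dose.

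Table 23 labels the first two rows by dose received, while Visit 07 is scheduled from birth. The SAP does not say which governs. The 6-month row carries no dose label, so the gap is clearest there.

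**3. Planning values.** Protocol Table 10 gives PT after the third DTwP dose as GMC 28.8 (log SD 0.68) with maternal Tdap and 43.2 (0.65) without. GMC × exp(±t × SD/√n) at n = 133 gives 25.6–32.4 and 38.6–48.3, against 25.6–32.3 and 38.6–48.3 in the table. The ratio is 28.8/43.2 = 0.667.

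**4. Illustration: keeping or excluding off-schedule infants.** The off-schedule share f and their GMC u are assumptions; the documents give neither. For an arm with planning GMC G and log SD s:

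- mean = (1 − f) ln G + f ln u
- variance = s² + f(1 − f)[ln(G/u)]²
- Welch 95% CI for the difference, then exponentiate.

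Scenario A: u is the same in both arms (5 to 25). Scenario B: u is 50% to 80% of the infant's own arm GMC. Half of each arm less 15% gives 133/2 × 0.85 ≈ 57 and 67/2 × 0.85 ≈ 28 at 18 weeks. All infants less 15% gives 113 and 57 at 6 months, with the post-third-dose values as a stand-in.

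Example (18 weeks, f = 0.10, u = 15): the log difference is 0.9 × ln(28.8/43.2) = −0.365, ratio 0.694. The variances are 0.501 and 0.523, SE = √(0.501/57 + 0.523/28) = 0.166, CI 0.50–0.97.

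| Time, f | A, kept | B, kept | Excluded |
|---|---|---|---|
| 18 wk, 5% | 0.680 (0.47–0.98 to 0.50–0.93) | 0.667 (0.49–0.91) | 0.667 (0.49–0.91), n = 54/27 |
| 18 wk, 10% | 0.694 (0.46–1.05 to 0.51–0.95) | 0.667 (0.48–0.92 to 0.49–0.91) | 0.667 (0.48–0.92), n = 51/25 |
| 6 mo, 10% | 0.694 (0.52–0.93 to 0.56–0.86) | 0.667 (0.53–0.83 to 0.54–0.83) | 0.667 (0.53–0.83), n = 102/51 |

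Paired intervals run from the lowest u to the highest. At f = 20%, scenario A gives 0.723. GMC 5 at 18 weeks stands for an undosed infant and applies only if rows follow visit age; under dose-based rows that infant has no value.

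**5. The perinatal-sample rule at 6 months.** With all 200 infants (133/67), the log-scale CI half-width is 0.196. If 5%, 10% or 15% lack the sample, 10, 20 or 30 infants are dropped (126/64, 120/60, 113/57). The half-width becomes 0.200, 0.207 or 0.212, which from unrounded values is 2.5%, 5.6% or 8.6% wider.

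**6. The birth cofactor analysis.** Using birth PT 68.8 (log SD 0.78), dropping 10% of 133 leaves 120 and moves the CI from 60.2–78.6 to 59.8–79.2. Dropping 30% leaves 93 and gives 58.6–80.8. Precision hardly changes; the fault is selection on events after the measurement.

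**The case against.** The strongest opposing case is that little depends on this. The study is described as estimation without a formal hypothesis, ITT and PP results are shown side by side, and no document ranks Table 24 or attaches a decision to it. The illustration rests on assumed rates. In scenario B keeping off-schedule infants costs nothing, and excluding them gains no precision. The CI reaching past 1 at 10% needs the low end of scenario A.

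Exposure may also be small. The 6-week visit is the day of the first DTwP, so dose 1 is largely controlled. Protocol 7.4.2.2.1 posts an on-call team near the delivery room to collect cord blood, and its remark on same-day discharge concerns colostrum. Missing data are expected to be minimal. The exploratory exclusions do suit the post-DTwP cytokine analyses. SAP 7.2 speaks only of review for possible exclusion, which can be read as feeding the exploratory set, and Listing 4 will show every exclusion.

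All of this limits the likely size, and it stands as such. It does not change the rule. The Table 12 footnotes tie each exclusion to one tier, SAP 7.2 does not override them, and a good fit to the cytokine tables does not repair Tables 24, 40 and 44. One further point also stands: excluding infants on dosing after randomisation can itself introduce selection, so a corrected PP table supports the ITT result and does not replace it.

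**Conclusion.** The concern holds. Followed exactly, the written rule builds the wrong infant PP set for a secondary analysis and for an exploratory one. This follows from the text and needs no assumption.

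The numerical effect is unknown in size and direction. Under the assumptions shown, 10% off-schedule infants move the PT ratio from 0.667 to 0.694 if they show no arm difference, and leave it unchanged if the arm ratio persists in them. The perinatal-sample rule widens the 6-month interval by about 2.5% to 9% for losses of 5% to 15%. The ITT tables are unaffected. It should be fixed because Table 24 cannot serve the purpose its label implies, and the correction is a matter of wording.

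**What to change.** Define the infant PP set by time point, for every tier:

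- **Birth:** valid perinatal sample; no DTwP-timing exclusion.
- **6 weeks:** in-window sample taken before any DTwP.
- **10 weeks, 18 weeks and 6 months:** DTwP doses due by that visit received in window, sample in window, no interfering product; no perinatal-sample requirement.

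State whether the 10- and 18-week rows are filled by dose received or by visit age. Visit windows in days already exist; what is missing is a definition of the appropriate DTwP window and of substantially out of window. Bring Protocol 11.4.1, SAP 6.3.2, SAP 7.2 and the Table 12 footnotes into line before unblinding.

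The cost is wording. Infant vaccinations are already recorded to the day-180 visit, so no new data are needed. The post-DTwP PP set loses off-schedule infants and regains correctly dosed infants without a perinatal sample, so it may be slightly smaller. The change does not remove the 18–38 day spread after dose 1, which arises with every visit in window. ITT is unchanged.

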11.2.2. Study Population

200 healthy pregnant women, ages 18 through 39 years, inclusive, who meet all eligibility criteria, and their infants.

Based on the accrual rate for similar studies, it seems reasonable to expect that the sites will be able to enroll this study in a timely fashion. Prior experience suggests up to 15% of subjects may be excluded from the per protocol analysis for the primary immunogenicity outcome either because they were lost-to-follow-up or otherwise do not have data available following the study vaccination, or because they had a protocol deviation requiring their exclusion from the per protocol analysis.

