Infants born to the pregnant subjects will have 4 study visits: at birth, at approximately 6 weeks of age (day of first DTwP), at approximately 10 or 18 weeks of age (one month after first or third dose of DTwP, respectively), and at 6 months of age.

Blood and colostrum/breast milk samples for immunologic assessments will be collected as described below:

- Pregnant subject: approximately 20 mL of blood will be collected on Study Day 1 (prior to vaccination), Study Day 31 (one month after vaccination), at delivery, and at 6 months postpartum in all women.
- Infants: up to 30 mL of umbilical cord blood will be collected at delivery and 5 mL peripheral blood will be collected at 6 weeks (prior to first dose of DTwP), either the 10-week or 18-week (per randomized study schedule), and 6 months of age in all infants. If cord blood cannot be obtained, 2-5 mL of peripheral blood will be collected by venipuncture within 72 hours of birth, before discharge, when possible. Cord blood is preferred over venipuncture.
- At delivery, and at the 6-week, either the 10-week or 18-week (per randomized study schedule), and the 6-month postpartum visit, a 10-20 mL sample of colostrum or breast milk will be collected. When possible, the first breast milk or colostrum collection will occur while the mother and baby are admitted for delivery and postpartum care. When not possible, it may be collected any time within the first 4 days of life.

Safety will be monitored from the time of signing of the ICF until trial termination.

See [Table 1](#) and [Figure 1](#) for study design.

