#### 6.3.1. Intention-to-Treat Analysis (ITT) Population

The maternal intent-to-treat (ITT) population for immunogenicity analyses includes all pregnant women who received the study vaccination.

The infant ITT population for immunogenicity analyses includes all infants born to women who received the study vaccination.

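### Apart from blood drawn after 72 hours, the infant per-protocol set for PT at birth equals the infants analysed as ITT, and a mother's disqualifying deviation does not remove her infant

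*SAP*

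**What the plan says.** SAP section 6.3.1 defines the wider set: "The infant ITT population for immunogenicity analyses includes all infants born to women who received the study vaccination". SAP section 6.3.2, with the same text in protocol section 11.4.1, then says that the infant per-protocol (PP) population for primary and secondary "immunogenicity analyses includes all infants in the ITT subset who have a blood sample from the perinatal period". A bracket that follows limits this to "cord blood or drawn blood within the 72 hours after birth". No condition on the mother appears.

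The maternal PP population does carry such conditions. All of a woman's data go if she was "Found to be ineligible at baseline". Data from visits after a major deviation also go. The examples given are a non-study licensed vaccine inside the exclusion windows and "Receipt of immunosuppressive therapy (e.g., corticosteroids) within 30 days prior to or after study vaccination".

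SAP Table 12 lists the reasons for leaving infant PP. Only one applies to the primary and secondary analyses: "Did not contribute a valid perinatal blood sample". The other three are footnoted as exploratory only.

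Two other places expect more. Protocol section 11.2.2 and SAP section 5 allow for up to 15% of subjects being left out of the PP analysis of the primary immunogenicity outcome, through loss to follow-up or missing data, "or because they had a protocol deviation requiring their exclusion from the per protocol analysis". SAP section 7.2 names a mother's non-study vaccine and a mother's immunosuppressive therapy among the major deviations to be reviewed for possible exclusion from the per-protocol population. It does not say whether the maternal or the infant population is meant.

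**The concern.** Protocol section 2.1.3 gives transplacental transfer of maternal IgG as the purpose of vaccinating in pregnancy. PT antibody measured at birth is therefore the mother's antibody, and whatever disturbed her response also disturbs the infant's birth titer. Under the written rules, a woman given immunosuppressive therapy in the stated window is dropped from the maternal PP GMC at delivery, yet her infant's cord titer stays in the PP comparison of the primary endpoint.

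The plan therefore shows ITT and PP results for PT at birth side by side, although the two are nearly the same analysis by construction. If they agree, that says almost nothing about the influence of maternal deviations, because those deviations are in both.

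**Working it through.** **1. The plan's own figure.** SAP Table 4 gives infant PT at birth a GMC of 68.8 and a log-scale SD of 0.78. The interval is GMC × exp(± t(0.975, n−1) × SD/√n).

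- n = 133: 1.978 × 0.78/√133 = 0.134, giving 60.2 to 78.7, as stated.
- n = 67: the lower limit comes to 56.9, against 56.8 stated.

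This point disputes neither figure. They serve in step 4 to judge the cost of a smaller PP set.

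**2. The two sets at birth.**

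- ITT as analysed: mother vaccinated, and a birth result exists. SAP Table 21 counts subjects with results at the time point, and SAP section 6.5 rules out imputation.
- PP: mother vaccinated, and a sample from cord blood or drawn within 72 hours.
- Difference: infants with a birth result from blood drawn after 72 hours. Such samples can exist, because peripheral blood is to be "collected by venipuncture within 72 hours of birth, before discharge, when possible".

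Mis-randomization does not separate the sets either, because SAP section 6.3 analyses all populations by product received. Table 12 speaks of a valid sample without defining the word. I read it as the condition in section 6.3.2.

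| Event in the mother | Maternal PP | Infant PP, PT at birth |
|---|---|---|
| Ineligible at baseline | all visits removed | titer stays |
| Non-study vaccine in window | later visits removed | titer stays |
| Immunosuppressive therapy in window | later visits removed | titer stays |

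**3. How many infants.** The documents give no rates, so these are assumptions: missing birth samples m = 5% to 15%, maternal deviations d = 2% to 10%, the two independent, and 200 mother-infant pairs.

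- Infants with a birth result: 200 × (1 − m) = 190, 180 or 170 at m = 5%, 10% or 15%. With no late samples, PP n equals ITT n in each case.
- Infants of deviating mothers among them: 200 × (1 − m) × d. The lowest value is 200 × 0.85 × 0.02 = 3.4, and the highest is 200 × 0.95 × 0.10 = 19. Section 6.3.2 removes none of them for the mother's deviation.
- If 2% of samples were drawn late (also assumed), PP would be smaller by 200 × 0.85 × 0.02 = 3.4 to 200 × 0.95 × 0.02 = 3.8 infants.

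**4. Precision if PP shrinks.** Under the plan's own 15% allowance, 133 × 0.85 = 113 and 67 × 0.85 = 57. At n = 113 the interval in step 1 becomes 59.5 to 79.6. With SD 0.78 in both arms, 80% power and two-sided alpha 0.05, the detectable Td/BOOSTRIX GMC ratio is 0.72 at 133/67 and 0.70 at 113/57.

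**The case against.** **The 72-hour limit.** A reader might infer that the PP analysis simply repeats ITT, removes no deviation at all, and must give identical PT-at-birth results in SAP Tables 21 and 22. The documents do not support that. The 72-hour limit is a real timing exclusion, and a late sample counts in ITT but not in PP. The route is narrow, since the birth visit window is itself +3 days, and it does not address anything that happened to the mother.

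**SAP section 7.2.** It can be said that the plan already provides for maternal vaccine and immunosuppressant deviations. This stands in part: it would be wrong to say that the plan is silent. But section 7.2 promises only a review, names no population, omits ineligibility, and has no counterpart among the infant reasons in Table 12.

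**The 15% allowance.** A reader might set 15% × 200 = 30 planned exclusions (20 BOOSTRIX, 10 Td) against none for maternal deviations. That comparison fails. The 15% is a ceiling for all causes, including loss to follow-up and missing data, and the share due to deviations is not given.

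**Small numbers, modest use.** Exclusion criteria 8 and 14 already bar immunosuppressive therapy and other vaccines received or planned in the windows, so deviations may be few. They do not rule out therapy started or a vaccine given after the study dose. It is also true that no passage calls the PP analysis a robustness check, that the study tests no specific null hypothesis, and that Table 12 would show that no maternal reason was applied. This lowers the stakes but leaves the conflict in the definitions.

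**Conclusion.** The point holds in this form. At birth, the infant PP set and the infants analysed in ITT can differ only through blood drawn after 72 hours, and no infant leaves because the mother was ineligible or had a major deviation. That contradicts the deviation-based exclusions expected in SAP section 5 and protocol section 11.2.2, and leaves SAP section 7.2 without a defined target.

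The size is unknown. The range of about 3 to 19 infants rests wholly on the assumed rates, and no shift in the GMCs or in the treatment comparison can be derived from the documents. The conclusion is also specific to the birth time point. At 6 weeks, an infant with a result but no perinatal sample is in ITT and not in PP, so a general statement that the infant PP tables duplicate the ITT tables would go too far.

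The change should be made before database lock. It concerns the meaning of the PP result for the primary endpoint. The ITT result is unaffected.

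**What to change.** In SAP section 6.3.2 and protocol section 11.4.1, add to the infant PP definition for the birth and 6-week samples: exclude an infant whose mother was found ineligible at baseline, or who had, before that sample, a major deviation as already defined for maternal PP, with the same vaccine and immunosuppressive-therapy windows. Do not carry over the exclusions for missing maternal results, since the absence of the mother's titer does not invalidate the infant's.

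Add the matching reason rows to SAP Table 12. Reword SAP section 7.2 to say which PP population each listed deviation affects, and add maternal ineligibility. Listing 4 already has an open column for the reason and needs no change.

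The cost is a change of wording, one derivation from data already collected, and a slightly smaller PP n. No visit, sample or participant procedure changes.
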